4.2 Survival Follow-up

	Survival Follow-up				
	q. 3 months until PD	At PD	After PD q. 3 months	Death	New Primary
Survival Follow-up	X	X	X	X	At each occurrence

1. If a patient is still alive 5 years after registration, no further follow-up is required.

5.0 Stratification Factors OR Grouping Factor

None.

6.0 Enrollment Procedures

- 6.1 Call the GI clinical research coordinator/PI for slot reservation.
- 6.2 Correlative research is mandatory in this trial and the subject will automatically be registered to this component (see Sections 3.19d, 3.19e 14.0, 17.31, 17.32, and 17.34). Please contact PI if there are any questions or concerns or exceptions.
- 6.3 Documentation of IRB approval must be on file before an investigator may enroll any patients.
- 6.4 Prior to enrollment, verify the following:
 - IRB approval
 - Patient eligibility
 - Existence of a signed consent form
 - Existence of a signed authorization for use and disclosure of protected health information
- 6.5 Treatment cannot begin prior to screening and must begin \leq 21 days after screening.
- 6.6 Pretreatment tests/procedures (see Section 4.0) must be completed within the guidelines specified on the test schedule.
- 6.7 All required baseline symptoms (see Section 10.3) must be documented and graded.
- 6.8 Treatment on this protocol must commence at University of Iowa Holden Comprehensive Cancer Center institution under the supervision of a medical oncologist.
- 6.9 Case has been discussed or an interventional oncologist has seen the patient and confirms the patient is a suitable candidate for this study.
- 6.10 Study drug is available on site.
- 6.11 Blood draw kit is available on site.

7.0 Protocol Treatment

7.1 Treatment Schedule

Use actual weight or estimated dry weight if fluid retention. Quality Control and Definitions of Deviations will be done according to the guidelines in Appendix IV

7.1.1 Treatment medication table

Agent	Dose Level	Route	ReRx
Durvalumab	750 mg	IV	q2w*

Cycle= 14 days

Note: All cycles will be based on durvalumab given once at least two weeks apart. The number of durvalumab doses are dependent on the cohort assigned during dose escalation.

*Refer to table 1 section 1.23 to see the number and timing of durvalumab immunotherapy administrations.

7.1.2 Treatment table for Y-90 Radioembolization (Y90-RE)

Agent	ReRx
TheraSpheres™	Per Table 1 section 7.4.1

Cycle= 14 days

Note: Y90-RE is administered 2 weeks post first durvalumab dose administration with cycle 2 of Durvalumab. The immunotherapy dose is prior to the Y90-RE. The immunotherapy does not have to be the same day as long as it is prior to Y90-RE.

Note: The Y90-RE dose and administration will be as per the FDA approved USPI for each patient. Goal is to deliver an ablative radiation dose to the targeted region and trigger a release of neo-antigens in order to augment immunotherapy; all the while minimizing collateral damage by sparing normal liver parenchyma. Per package insert, recommended Y90-RE dose is 80 Gy to 150 Gy per lobe of liver; this is intended to prevent radioembolization-induced liver disease (REILD). Upper limit for dose administration is also determined by the lungs, which may receive an estimated dose of no more than 30 Gy from a single administration nor a cumulative total of 50 Gy from multiple administrations.

As noted in the protocol, there are numerous dosing methods in place for Durvalumab.

7.2 Return to consenting institution

For this protocol, the patient must return to the consenting institution for evaluation at least every 14 days during treatment and every 90 days during clinical follow-up (Active Monitoring Phase).

7.3 Treatment by local medical doctor (LMD)

Treatment by a local medical doctor (LMD) is not allowed.

7.4 Phase I – determination of Maximum Tolerated Dose (MTD)

7.4.1 Dose Escalation

Dose level	Immunotherapy (Durvalumab) Administrations						Number of Durvalumab Administrations (total)	
	Prior to Y90-RE		Y-90 Radioembolization (Y90-RE)	Post Y90-RE				
	Week -2	Week 0		Week 2	Week 4	Week 6		
-2					X		1	
-1				X	X		2	
1 (start)	X	X					2	
2	X	X		X			3	
3	X	X		X	X		4	
4	X	X		X	X	X	5	

7.4.1.1 Treatment by a local medical doctor is not allowed. All patients to be treated at University of Iowa.

7.4.1.2 Investigators are to contact the Study Chair as soon as any dose-limiting toxicity (DLT) occurs.

7.4.2 Definitions of Dose Limiting Toxicities (DLT)

A DLT will be defined as any Grade 3 or higher treatment-related toxicity that occurs during the DLT observation phase (8 weeks post Y90-RE), including:

- Any event resulting in a delay of cycle 2 by \geq 14 calendar days
- Any Grade 4 immune related adverse event (irAE)
- Any Grade 3 immune related AE (irAE) that does not resolve to \leq Grade 1 or to baseline with immunosuppressive therapy within 3 weeks
- Any Grade 3 colitis
- Any Grade 3 noninfectious pneumonitis irrespective of duration
- Grade 4 neutrophil count decreased lasting longer than 5 calendar days
- Grade 4 platelet count decreased
- Grade 3 platelet count decreased with hemorrhage
- Any \geq Grade 2 pneumonitis that does not resolve to \leq Grade 1 within 7 days of the initiation of maximal supportive care
- Any other Grade 3 irAE (excluding colitis or pneumonitis), that does not downgrade to Grade 2 within 7 days after onset of the event despite optimal medical management including systemic corticosteroids or does not downgrade to \leq Grade 1 or baseline within 14 days
- Liver transaminase elevation $> 8 \times$ ULN
- Total bilirubin $> 5 \times$ ULN
- AST or ALT $> 5-8 \times$ ULN with concurrent increase in total bilirubin $> 2 \times$ ULN without evidence of cholestasis or alternative explanations, e.g., viral hepatitis, disease progression in the liver, etc. (Hyll's Law). Exception: If it is present at cycle 3 but resolves at cycle 4 it is not a DLT.
- Any \geq grade 3 non-hematologic toxicity, except:
 - Grade 3 nausea or vomiting that lasts < 48 hours and resolves to \leq Grade 1 either spontaneously or with conventional medical intervention
 - Grade 3 nausea, vomiting, and diarrhea lasting < 72 hours in the absence of maximal medical therapy
 - Grade 4 vomiting and diarrhea lasting < 72 hours in the absence of maximal medical therapy
 - Grade 3 hypertension in the absence of maximal medical therapy
 - Grade 3 metabolic abnormalities (e.g. hypokalemia, hypomagnesemia, hypocalcemia, hypophosphatemia) that recover to \leq Grade 1 within 48 hours
 - \geq Grade 3 electrolyte abnormality lasting < 72 hours, is not clinically complicated, and resolves spontaneously or responds to conventional medical intervention.
 - Grade 3 or 4 elevation in serum amylase and/or lipase that are not associated with clinical or radiographic evidence of pancreatitis.
 - Grade 3 rash < 5 calendar days
 - Grade 3 rash that resolves to \leq Grade 1 within 3 weeks
 - Grade 3 fatigue lasting ≤ 7 days
 - Grade 3 endocrine disorder (thyroid, pituitary, and/or adrenal insufficiency) that is managed with or without systemic corticosteroid therapy and/or hormone replacement therapy and the subject is asymptomatic

- Grade 3 inflammatory reaction attributed to a local antitumor response (e.g., inflammatory reaction at sites of metastatic disease, lymph nodes)
- Concurrent vitiligo or alopecia of any AE grade
- Grade 3 infusion-related reaction (first occurrence and in the absence of steroid prophylaxis) that resolves within 6 hours with appropriate clinical management
- Grade 3 or 4 neutropenia that is not associated with fever or systemic infection that improves by at least 1 grade within 7 days. Grade 3 or Grade 4 febrile neutropenia will be a DLT regardless of duration or reversibility

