1.4.5 Rationale for Durvalumab Dose Escalation

The trial, for each subject, will consist of a screening period, a treatment and observation phase. The treatment phase is approximately 2 months with Y90-RE in combination with fixed dose durvalumab and **the dose limiting toxicity (DLT) observation phase for 8 weeks post Y90-RE**. The rationale for the proposed dosing schema is keeping in mind the timing of toxicities that are typically seen post Y90-RE. Most patients have elevation of their liver enzymes the first 1-2 weeks. Therefore, with the dosing escalation, we did not include the added dose at week 2 for the first dose escalation (see dose level table – section 7.41 and Table 1 section 1.23 below). Patients get fixed dosing of immunotherapy, which is the case for all immunotherapy-based studies. Depending on the dose level, patients can get a maximum of 2 doses before and 3 doses post Y90-RE. As noted in Table 1 (section 1.23 below), while dose level 1 and dose level -1 have the same number of durvalumab administrations, they are different since dose level 1 get 2 doses pre-Y90-RE ('priming doses of immunotherapy before Y90-RE) while dose level -1 only get 2 doses post-Y90-RE.

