1.4.6 Study Design

This clinical trial will be conducted as a single-center, open-label, Phase I trial to evaluate the feasibility and safety of Y90-RE in combination with a fixed dose of durvalumab in subjects with liver-predominant, mCRC. It can be offered in the refractory setting and/or more so integrated into the current standard systemic chemotherapy ± biologics, by focusing on enhancing the effect of Y90-RE with immunotherapy. Therefore, there is the option for patients with significant liver-predominant disease burden that are considered candidates for Y90-RE to temporarily discontinue their current chemotherapy in order to participate within this trial. Subjects will be approached for screening at outpatient clinic visit appointments and interested qualified subjects will be consented and offered participation in this trial. Once consent has been obtained, for eligible subjects, baseline values will be established, and subjects will begin treatment and be followed-up for the next three months. The washout period to begin treatment (cycle 1 day 1) for

this clinical trial will be at least 2 weeks after prior chemotherapy or biologic. Screening can begin prior. The goal is to keep the duration on the clinical trial minimal.

The trial, for each subject, will consist of a screening period, a treatment and observation phase. The treatment phase is approximately 2 months post-Y90-RE in combination with fixed dose durvalumab. The DLT observation phase will be for 8 weeks post dose of Y90-RE.

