1.4.7 Number of Subjects

This clinical trial will recruit 18 subjects. The estimated recruitment rate is at least one subject every 1-2 months, in which a minimum of 12-18 subjects will be enrolled over a period of 18-24 months. The number of subjects in the dose escalation will depend on the number of dose levels needed to determine the MTD or confirm the current dosing for durvalumab can be used in combination with Y90-RE. **The dose limiting toxicity (DLT) observation phase is 8 weeks post Y90-RE.**

In the expansion cohort, the remaining subjects (from the total 18 subjects) will be treated at the MTD dose of the combination of Y90-RE and durvalumab. Since all patients received immunotherapy and Y90-RE, they would be included in the evaluation of efficacy objectives and correlative components of the study.

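### The DLT window in 7.4.2 opens at Y90-RE, but its first listed item arises before Y90-RE, so some cycle 1 toxicity at levels 1 to 4 has no stated DLT status

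*Combined protocol and SAP*

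**What the plan says.** The lead sentence of 7.4.2 reads "A DLT will be defined as any Grade 3 or higher treatment-related toxicity that occurs during the DLT observation phase (8 weeks post Y90-RE"). The same anchor is in 1.4.5 ("the dose limiting toxicity (DLT) observation phase for 8 weeks post Y90-RE"), 1.4.6 ("The DLT observation phase will be for 8 weeks post dose of Y90-RE") and 1.4.7 ("The dose limiting toxicity (DLT) observation phase is 8 weeks post Y90-RE"). Section 17.2 requires 8 weeks of observation after Y90-RE before new patients are treated.

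The list under the lead sentence begins with "Any event resulting in a delay of cycle 2 by" at least 14 calendar days. It also contains "Any Grade 3 noninfectious pneumonitis irrespective of duration". Among the exceptions is "Grade 3 fatigue lasting" no more than 7 days.

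On timing, 7.1.2 states: "Y90-RE is administered 2 weeks post first durvalumab dose administration with cycle 2 of Durvalumab". The test schedule in 4.1 and the dose table in 7.4.1 agree: at levels 1 to 4, durvalumab is given at week -2 and week 0, with the second dose before Y90-RE.

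Under 1.4.6 and 17.2, one patient is treated per level until the first DLT. Two more are then added at that level and the trial changes to 3+3. Section 13.8 replaces a patient who does not complete cycle 1 before Y90-RE, unless the reason is toxicity.

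**The concern.** The list is introduced as part of what happens in the 8 weeks after Y90-RE, yet its first item concerns a visit that includes Y90-RE. An event that holds up that visit normally comes before the window opens. No section opens the DLT window at the first durvalumab dose; 10.2.2 does so for adverse event collection only.

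The first item may be a deliberate way of bringing cycle 1 into the definition. Even so, it does not settle every listed cycle 1 toxicity. In the accelerated phase a single patient decides each level, so whether one event counts determines whether the next step is two more patients or the next dose level.

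**Working it through.** **Timeline, levels 1 to 4 (4.1, 7.1.2, 7.4.1).** Day 0 is the first durvalumab dose, day 14 is cycle 2 with Y90-RE, and the window runs for the next 56 days. The part before the window is 14 / (14 + 56) = 14/70 = 20% of the nominal span. A delay of up to 13 days does not meet the first item, so the uncovered interval can reach 14 + 13 = 27 days.

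**Case (a): a listed event that resolves.** Take treatment-related Grade 3 fatigue from day 3 to day 12, which lasts 9 days and so exceeds the 7-day exception. After Y90-RE it would be a DLT. In cycle 1 the window is closed, and the delay to cycle 2 is max(0, 3 + 9 - 14) = 0 days.

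More generally, let onset be day d (0 to 13) and time to Grade 0-1 be L days. Table 8.21 allows 2 weeks for other non-hematologic Grade 3 events, so L is at most 14. The delay is max(0, d + L - 14), at most 13 + 14 - 14 = 13 days, one short of the item. This assumes that the 2 weeks run from onset, which the table does not state. If they run from the day treatment is held (day 14), the delay can reach 14 days and the item is met. The fatigue example does not depend on this.

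Steroid-treated immune events behave differently. Where Appendix VII allows restart, it generally requires a completed taper of at least 28 days. Restart is then no earlier than day 28, at least 28 - 14 = 14 days late, and the first item catches the event. Case (a) is therefore mainly events with no taper-related hold.

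**Case (b): an event that ends treatment.** Table 8.21 permanently stops all protocol treatment for Grade 3 pneumonitis, and 8.0 asks that the table be followed strictly in the first two cycles. If this happens after dose 1, Y90-RE is not given and the window never opens. The 8-week wait in 17.2 has no starting point either. The event counts only if a cycle 2 that never happens is read as a delay of at least 14 days, which the text permits but does not say. Section 13.8 implies that the patient is not replaced, without giving DLT status.

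**Effect on escalation.** Suppose there is one such event, no other DLT, and level 4 confirmed in 6 patients.

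| Event | Patients to MTD | Left of 18 |
|---|---|---|
| Not counted | 1+1+1+6 = 9 | 9 |
| Counted at level 1 | 6+3+3+6 = 18 | 0 |
| Counted at level 2 | 1+6+3+6 = 16 | 2 |
| Counted at level 3 | 1+1+6+6 = 14 | 4 |

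The first row agrees with the 9 evaluable patients in 17.3. In the other rows, the level with the event is tested in 6 patients instead of 1.

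**Illustration only.** The documents give no cycle 1 DLT rate. If each patient had an assumed probability q of an uncounted event, the chance of at least one among the three single patients at levels 1 to 3 is 1 - (1 - q)^3: 3%, 14% and 27% for q = 1%, 5% and 10%. These values of q are not estimates for the narrow class in cases (a) and (b).

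**The case against.** The strongest reply is that the anchor is intended. It is repeated in three other sections, the primary goal concerns the combination, and the cycle 2 item then serves as the route by which cycle 1 counts. That route is wide: it reaches most immune toxicity treated with a steroid taper, and a cycle 2 that is never given is readily read as delayed. This stands, and it narrows the gap. It does not close it, because case (a) falls outside the item and case (b) depends on an unstated reading.

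A reader might infer more than the documents support:

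- **That early toxicity goes unseen.** It does not. Adverse events are collected from first treatment (10.2.2), the team checks for them and judges relatedness before each durvalumab dose (8.1), Grade 3 and higher events are attributed to both agents (10.2), and routine events are captured for the investigator, the IDE sponsor and the DSMC (10.5.1). Only the timing of DSMC review of a non-serious event is uncertain.
- **That 17.5.3 removes the case (b) patient from escalation.** Its replacement rule is worded for the assessment of efficacy.
- **That one uncounted event decides the move to level -1.** Section 17.2 requires more than one DLT in 3 or in 6 patients for that.
- **That levels 1 to 4 are mis-ranked.** The schedule before Y90-RE is the same at all four.

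**Conclusion.** The inconsistency is plain in 7.4.2 and should be corrected. It is confined to levels 1 to 4, since levels -1 and -2 have no durvalumab before Y90-RE. It concerns listed, related, non-exempt Grade 3 or higher cycle 1 events that either resolve without a 14-day delay or end treatment before Y90-RE.

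Followed literally, the definition can let a single-patient level escalate on an event that would be a DLT after Y90-RE. The level is then tested in 1 patient instead of 6, assuming no further DLT. In that scenario level 4 is the MTD whether or not the event is counted. What is lost is the evidence behind an escalation step; a wrong MTD is not shown. How often this would happen cannot be derived from the documents.

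**What to change.** Reconcile 7.4.2 (with the repeated text in 1.4.5, 1.4.6 and 1.4.7), 13.8 and 17.2.

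1. State that a toxicity on the protocol's own DLT list that prevents Y90-RE counts as a DLT, and that the patient stays in the escalation denominator.
2. For other cycle 1 toxicity, choose one consistent rule and state it. One option is to count DLTs from the first study dose through 8 weeks after Y90-RE, which fits the cycle 2 item and the start of collection in 10.2.2. The other is to keep the post-Y90 anchor, say that the cycle 2 item is an exception to it, and say how other cycle 1 events enter the escalation decision. The choice is the sponsor's.

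The cost is wording; no new data collection is needed. The observed DLT rate may look slightly less favourable, and a toxicity due to durvalumab alone could start 3+3 earlier. In the scenario above, that leaves 0, 2 or 4 expansion places instead of 9. The loss is softened because 17.3 frames the expansion objective irrespective of dose level, and 1.4.7 includes all patients in the efficacy and correlative work. Each added cohort takes at least about 2 + 8 = 10 weeks. Doses, the DLT list and treatment-stopping rules stay as they are.

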8.2 Treatment schedule modifications for durvalumab

Adverse events (both non-serious and serious) associated with durvalumab exposure may represent an immunologic etiology. These adverse events may occur shortly after the first dose or several months after the last dose of treatment. Durvalumab must be withheld for drug-related toxicities and severe or life-threatening AEs per Table 8.21 below. See Section 9.0 for supportive care guidelines, including use of corticosteroids.

Table 8.21 Dose Modification Guidelines for Drug-Related Adverse Events for Durvalumab			
CTCAE System/Organ/Class	Adverse Event	Grade	Action
Gastrointestinal disorders	Diarrhea or Colitis	2	Hold all protocol treatment until Grade 0-1. If AE does not resolve to Grade 0-1 within 2 weeks, then permanently discontinue all protocol treatment
		3, 4	Permanently discontinue all protocol treatment
Investigations	Alanine aminotransferase increased, Aspartate aminotransferase increased, and blood bilirubin increased	2	Hold all protocol treatment until Grade 0-1. If AE does not resolve to Grade 0-1 within 2 weeks, then permanently discontinue all protocol treatment
		3-4	Permanently discontinue all protocol treatment
Metabolism and nutrition disorders	Glucose intolerance (Type 1 diabetes mellitus [if new onset]) or Hyperglycemia	T1DM or 2-4	Hold all protocol treatment until clinically and metabolically stable.

Table 8.21 Dose Modification Guidelines for Drug-Related Adverse Events for Durvalumab

CTCAE System/Organ/Class	Adverse Event	Grade	Action	
Endocrine disorders	Endocrine disorders-Other, specify: Hypophysitis	2-4	Hold all protocol treatment until Grade 0-1. If AE does not resolve to Grade 0-1 within 2 weeks, then permanently discontinue all protocol treatment	
	Hypothyroidism	2-4	Therapy with durvalumab can be continued while thyroid replacement therapy is instituted	
	Hyperthyroidism	2-3	Hold all protocol treatment until Grade 0-1. If AE does not resolve to Grade 0-1 within 2 weeks, then permanently discontinue all protocol treatment	
		4	Permanently discontinue all protocol treatment	
General disorders and administration site conditions	Infusion related reaction	1, 2	Follow infusion related reaction treatment guidelines (Table 9.21). Hold all protocol treatment until Grade 0-1. If AE does not resolve to Grade 0-1 within 2 weeks, then permanently discontinue all protocol treatment	

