13.8 Unevaluable patients

If a patient fails to complete the first cycle of treatment, prior to administration of Y-90, for reasons other than toxicity, the patient will be regarded as unevaluable and will be replaced.

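### The DLT window opens at Y90-RE, two weeks after durvalumab starts at levels 1 to 4: severe toxicity in between is not counted as written, and the cycle 2 delay item contradicts the window

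*Combined protocol and SAP*

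**What the plan says.** Section 7.4.2 opens its definition with: "A DLT will be defined as any Grade 3 or higher treatment-related toxicity that occurs during the DLT observation phase (8 weeks post Y90-RE". Section 1.4.6 repeats it ("The DLT observation phase will be for 8 weeks post dose of Y90-RE"), and sections 1.4.5 and 1.4.7 agree. The first listed item in 7.4.2 is "Any event resulting in a delay of cycle 2 by" 14 or more calendar days. A later item starts below Grade 3: "Grade 2 pneumonitis that does not resolve to" Grade 1 or lower within 7 days.

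On timing, section 7.1.2 says "Y90-RE is administered 2 weeks post first durvalumab dose administration with cycle 2 of Durvalumab", with the durvalumab dose coming first. Table 1 and section 7.4.1 give levels 1 to 4 a durvalumab dose at week -2 and another at week 0. Levels -1 and -2 have none before Y90-RE.

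For Grade 3-4 colitis, liver and pneumonitis events, Table 8.21 tells the team to "permanently discontinue all protocol treatment". Section 13.8 covers a patient who does not complete the first cycle: "prior to administration of Y-90, for reasons other than toxicity, the patient will be regarded as unevaluable and will be replaced". Section 17.5.3 treats a subject without Y90-RE as non-evaluable for efficacy and replaces that subject toward the 18. Section 17.2 requires at least 8 weeks of observation after Y90-RE before new patients are treated. It treats one patient per level until the first DLT, then adds two at that level and moves to 3+3.

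**The concern.** The priming doses of durvalumab are part of the regimen at levels 1 to 4, yet the stated window leaves out the time between the first of them and Y90-RE. The cycle 2 delay item can concern only that time, so the lead sentence and the list do not fit together.

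At stake is the escalation path. One event classified as a DLT ends the single-patient phase. The same classification feeds the step down from level 1 to level -1, and that step removes exactly the doses given before Y90-RE. If toxicity from those doses is not counted, the rule cannot respond to the problem that the step down would solve.

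**Working it through.** **The plan's own figures.** Section 17.2 gives at least 82% for seeing a toxicity of 25% incidence among 6 patients: 1 - 0.75^6 = 0.822, which reproduces. Section 17.3 expects 9 evaluable patients, which matches 1 + 1 + 1 + 6 (one patient at each of levels 1 to 3, six at level 4, no DLT). Neither is disputed. The second shows that three levels may be passed on one patient each.

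**Time not counted, levels 1 to 4.** Day 0 is the first durvalumab dose, Y90-RE is planned for day 14, and the window runs 56 days to day 70.
- On schedule: 14 / (14 + 56) = 14/70 = 20% of days.
- Cycle 2 given 5 days late (test schedule window): 19 / (19 + 56) = 19/75 = 25%.

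**The delay item.** A delay of 14 days puts cycle 2, and so Y90-RE, at day 14 + 14 = 28 or later. The window opens only once the delay is over. The item also names no reference date. Counted from nominal day 14, a DLT needs cycle 2 on day 28 or later; counted from the end of the visit window (day 19), on day 33 or later. The two disagree on days 28 to 32.

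**Three readings of 7.4.2.**
- The lead sentence governs the list: no event before Y90-RE is a DLT, and the delay item has no effect at levels 1 to 4.
- The delay item alone stands outside the window: a Grade 3-4 event that resolves without a 14-day delay is still missed.
- Every item stands outside the window: events before Y90-RE count, but the items then have no end date either. The list includes a general item for Grade 3 or higher non-hematologic toxicity, so the 8-week window would govern very little.

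**Patient stopped for good before Y90-RE.** Section 13.8 does not replace this patient if the reason is toxicity. Section 17.5.3 does, for efficacy and the sample of 18. The wait in 17.2 has no start date. No section says whether the patient is a DLT.

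**Illustration.** The documents give no event rate before Y90-RE, so the true DLT rate p and the share s of DLTs falling before Y90-RE are assumed. The counted DLT rate is c = p(1 - s) if those patients are kept as non-DLT, or c = p(1 - s)/(1 - ps) if they are replaced. A 3+3 level clears with probability (1 - c)^3 + 3c(1 - c)^5.

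| p | s | c, kept | clears, kept | c, replaced | clears, replaced |
|---|---|---|---|---|---|
| 0.33 | 0 | 0.330 | 43% | 0.330 | 43% |
| 0.33 | 0.05 | 0.314 | 47% | 0.319 | 46% |
| 0.33 | 0.10 | 0.297 | 50% | 0.307 | 48% |
| 0.33 | 0.20 | 0.264 | 57% | 0.283 | 53% |
| 0.20 | 0 | 0.200 | 71% | 0.200 | 71% |
| 0.20 | 0.05 | 0.190 | 73% | 0.192 | 73% |
| 0.20 | 0.10 | 0.180 | 75% | 0.184 | 74% |
| 0.20 | 0.20 | 0.160 | 79% | 0.167 | 78% |

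A single patient clears a level with probability 1 - c. At p = 0.33 that is 67% with nothing missed, and 69%, 70% or 74% on the kept reading.

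**The case against.** The strongest reply is that the list is wider than its lead sentence. The pneumonitis item starts at Grade 2, the delay item covers an event of any grade, and section 10.2 speaks of DLTs regardless of severity. A specific item that can concern only the time before cycle 2 is naturally read as a DLT in its own right, and a patient who never reaches cycle 2 arguably meets it. This stands in part. A reader might infer that toxicity before Y90-RE is never a DLT and that the delay item is inoperative; that follows on the first reading only. But no text gives the list priority, and on the second reading the gap narrows without closing.

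A second reply is that levels 1 to 4 share the same dosing before Y90-RE, so an event there is single-agent toxicity and cannot separate those levels. It is true that it cannot separate them. But the priming doses belong to each of these levels, and the move to level -1 takes them away, so the event bears on that decision.

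Third, adverse events are collected from the first treatment (10.2.2), serious ones reach the DSMC within one business day (10.5.3), and cumulative reports are compared with stopping rules (10.5). These events would therefore be seen. Being seen does not make them DLTs, and it is DLTs that drive the algorithm in 17.2.

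A reader might also infer that after a Grade 4 immune event on day 7 at level 1 the plan sends the next patient to level 2. It does not say so: the required wait runs from a Y90-RE that the patient may never receive, so 17.2 is silent. Nor do the documents establish that such a patient is kept as a non-DLT; 13.8 and 17.5.3 point in different directions.

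**Conclusion.** The concern holds for levels 1 to 4. The window stated in 7.4.2 and 1.4.5 to 1.4.7 leaves out the planned two weeks between the first durvalumab dose and Y90-RE, no section extends it back, and the section's own delay item conflicts with it. At least some severe events, and the status of a patient stopped before Y90-RE, are left to the team's reading at the point where one DLT changes the design. It should be fixed.

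The finding rests on the schedule. The clearance figures are illustrations: they depend on assumed rates and on whether the affected patients are kept or replaced. The 20% and 25% are shares of calendar days; the documents do not support reading them as shares of risk. Levels -1 and -2 are not affected.

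**What to change.** 1. In 7.4.2, and wherever 1.4.5 to 1.4.7 state the window, count DLTs from the first study treatment (durvalumab or Y90-RE) through 8 weeks after Y90-RE, at Grade 3 or higher unless a listed item states otherwise. Naming either treatment keeps the rule right at levels -1 and -2, where Y90-RE comes first.
2. In the delay item, state that the 14 days are counted from the nominal cycle 2 date and that the item applies at levels 1 to 4. Section 7.1.1 bases cycles on "durvalumab given once at least two weeks apart", so the meaning of cycle 2 is unclear at level -2, which has a single durvalumab dose.
3. In 17.2, state that a patient with a DLT before Y90-RE counts as a DLT at that dose level from the date of the event and is not replaced for escalation. In 17.5.3, note that replacement there is for efficacy only.

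The cost is a few sentences. No visits or procedures are added, because adverse events are already collected from the first treatment. Somewhat more events may count as DLTs, so escalation may use more of the 18 patients. The trial runs under an IDE, so the amendment needs FDA and IRB approval.
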